Stereotactic Radiosurgery, as defined by the American Society for Therapeutic Radiology and Oncology (ASTRO), the American Association of Neurological Surgeons (AANS), and the Congress of Neurological Surgeons (CNS), includes single dose SRS and well as HR delivered in 2-5 fractions over multiple days¹⁴⁻¹⁵. The majority of data supporting the use of SRS for the treatment of brain metastases has evaluated only single dose SRS and it is unclear whether the same results can be attributed to HR in 2-5 fractions. Brain metastasis amenable to single fraction SRS are typically defined as those measuring less than 3cm and producing less than 1cm of midline shift³. For brain metastasis not amenable to SRS, but for which focal brain radiation is indicated for boost or as salvage after WBRT or for avoidance of neurocognitive decline, HR provides an alternative treatment option. Current data describing the use and results of HR for the treatment of brain metastasis is limited to few retrospective series. Pater and colleagues from University of Cincinnati have demonstrated HR delivered to a dose of 30 Gy in 5 fractions to be effective and tolerable in a series of 34 patients, with a 6% (n=2) incidence of asymptomatic radiation necrosis and a 6 month actuarial local control rate of 68%¹⁶. A second series of 43 patients with metastatic breast cancer treated at Staten Island University Hospital utilized HR to a dose of 24 Gy delivered in 4 fractions, with a median survival from treatment of 7.5 months¹⁷. Recently, Wang et al. have reported on the use of HR in the setting of resected brain metastasis with resection cavities > 3cm and have demonstrated a local control rate of 80% at 6 months with the use of 24 Gy in 3 daily fraction¹⁸. With only a few series reported, the optimal dose and fractionation schedule is unknown.

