3.2 Enrollment/Randomization

This study will include 8 patient cohorts with 3 patients per cohort. The patients will be enrolled and treated following a Bayesian method permitting precise determination of the therapeutic working-dose while directly controlling the likelihood of an overdose. The method, known as Escalation with Overdose Control (EWOC), has been used to design phase I clinical trials at several cancer centers including the Fox Chase Cancer Center (PA), the Sylvester Comprehensive Cancer Center (FL), and the Winship Cancer Institute (GA) and pharmaceutical companies. EWOC was the first dose-finding procedure to directly incorporate the ethical constraint of minimizing the chance of treating patients at unacceptably high doses. Its defining property is that the expected proportion of patients treated at doses above the MTD is equal to a specified value α , the feasibility bound. This value is selected by the clinician and reflects his/her level of concern about overdosing.

The dose levels for the trial are summarized in Table 1. The dose for the first cohort of 3 patients in the trial will be the dose level 0, previous results indicating this to be a safe dose. The patient accrual will be suspended until the 4 month toxicity evaluation is completed for all previously enrolled patients. The dose for each subsequent cohort of 3 patients will be determined so that, on the basis of all available data and the target highest acceptable toxicity level of 25% DLT, the probability that it exceeds the MTD is equal to a pre-specified value α . In this trial, we set $\alpha = 0.25$ and increase α in small increments until $\alpha = 0.5$, this value being a compromise between the therapeutic aspect of the agent and its toxic side effects. The dose selected for every patient in the trial will be between the minimum dose of 27.5 Gy and the maximum allowable dose of 40 Gy. The trial will be terminated if 3 DLTs are observed in any cohort of 3 patients treated with the lowest dose level. The trial will stop after 24 patients have been enrolled and MTD will be estimated from one of the 6 specified dose levels listed in the Table 1. If no MTD is found because even the highest dose level is still considered under toxic, then the highest dose group will be considered the MTD and expanded to 12 patients.

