The enrollment will be done sequentially. If a grade 5 toxicity develops in the initial evaluation period (4 months), then the study will be halted and all patient data will be reviewed by the data safety monitoring committee to determine the likelihood that the treatment given was responsible and whether the study can resume. If a patient is not able to complete follow up to the toxicity assessment point of 4 months due to a toxicity judged not to be at least possibly related to therapy, then that patient will be replaced at the same dose level by the next patient enrolled into that cohort. After all patients in a designated dose group have completed the 4 month toxicity assessment, the documented DLTs, having previously been reviewed by the PI, co-investigators and data safety monitoring committee, will be again reviewed by the PI and co-investigators at the time the decision is made to escalate or de-escalate to the next dose level accordingly.

Example of sequential enrollment

Patients identified meeting eligibility criteria will be offered enrollment in this study. As with any other protocol, the risks, benefits, and alternatives of protocol enrollment will be

thoroughly discussed and patient consent form will be provided for further information. Once the patient agrees to be enrolled, they will be allocated to a specific dose level based on sequential enrollment. The first three patients assigned will be enrolled into dose level 1. Once this group has reached the accrual goal of three patients, then that cohort will be closed until the 4 month toxicity evaluation is completed for all 3 patients. The next three consecutive patients within that cohort will be enrolled to dose level 2 unless a grade 3 or 4 toxicity was documented (as detailed above). If there was such a toxicity, then the three next patients will be enrolled into the same dose level as an expansion.

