3.4.3 Total dose determination

1. Total dose determination will depend on the currently accruing dose level
2. Starting dose level is based on current institution standards and retrospective reports from other institutions^{15,19}.

Table 1. Summary of dose levels to be tested.

Dose level	Total Dose (Gy)	Dose per Fraction (Gy)	Fraction Number	BED ₁₀ (Early Effects)	BED ₃ (Late Effects)
-1	27.5	5.5	5	44	78
0	30	6	5	49	90
1	32.5	6.5	5	55	103
2	35	7	5	60	117
3	37.5	7.5	5	66	131
4	40	8	5	69	147
SRS*	18-21 Gy	18-21 Gy	1	53-68	126-168

*for comparison only, single fraction SRS will not be used in this protocol

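### The enrollment example in 3.2 starts cohort 1 one dose level too high and has no step down, contradicting the EWOC design it is meant to illustrate

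*Combined protocol and SAP*

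**What the plan says.** All of the following is in the combined protocol and SAP.

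- **Starting dose, design text (3.2).** The starting level is fixed in these words: "first cohort of 3 patients in the trial will be the dose level 0, previous results indicating this to be a safe dose".
- **Starting dose, worked example (3.2, Example of sequential enrollment).** "The first three patients assigned will be enrolled into dose level 1".
- **Meaning of the labels (3.4.3, Table 1).** Level -1 is 27.5 Gy, level 0 is 30 Gy, level 1 is 32.5 Gy and level 2 is 35 Gy, all in 5 fractions. The starting level rests on institutional practice and published series: "Starting dose level is based on current institution standards and retrospective reports from other institutions".
- **Later doses, design text (3.2).** "The dose for each subsequent cohort of 3 patients will be determined so that, on the basis of all available data" and a 25% DLT target, the probability of exceeding the MTD equals alpha. Alpha starts at 0.25 and rises in small steps to 0.5. The paragraph just before the example has the investigators review DLTs "at the time the decision is made to escalate or de-escalate to the next dose level accordingly".
- **Later doses, worked example (3.2).** The next three patients "will be enrolled to dose level 2 unless a grade 3 or 4 toxicity was documented". If one was, "then the three next patients will be enrolled into the same dose level as an expansion".
- **Numeric DLT stop (3.2).** The trial ends after 3 DLTs in a cohort of 3, but only at the lowest dose level.

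**The concern.** One section gives two sets of dosing instructions. The example is headed as an illustration but is worded as an instruction, and it is the only step-by-step account of how a patient gets a dose level. Staff who work from it would treat the first three patients one level above the dose the design text calls safe. They would also have no instruction to go down, however many patients in the cohort had a DLT. What is at stake is radiation dose to the brain in patients whose risk EWOC was chosen to limit.

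**Working it through.** **1. The plan's own figures.** 8 cohorts × 3 patients = 24, as stated. With BED3 = D × (1 + d/3), where D is total dose and d is dose per fraction:

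- level 0: 30 × (1 + 6/3) = 90
- level 1: 32.5 × (1 + 6.5/3) = 102.9, shown as 103

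Both match Table 1.

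**2. Starting dose.** The design text says level 0 and the example says level 1. The example's next step is level 2, also a Table 1 label, so nothing suggests that level 1 just means the first level used. The difference is 32.5 − 30 = 2.5 Gy (2.5/30 = 8%), and in BED3 102.9/90 = 1.14, or +14%.

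**3. Next dose.** The example has two branches: up one level, or the same level. It gives no toxicity count and no downward branch. Its cross-reference to the detail above may restrict the trigger to DLTs as defined in 2.1.2, but that adds no cap. The 3/3 stop applies only at 27.5 Gy, so it does not cover 3/3 at 30 or 32.5 Gy.

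**4. 3/3 DLTs, no prior needed.** The exact two-sided 95% lower limit is 0.025^(1/3) = 0.292, above the 0.25 target. For 2/3 the limit is 0.094, which is below the target, so this argument covers 3/3 only.

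**5. 3/3 and 2/3 under EWOC, illustration.** The documents give no priors, so these are assumptions:

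- logistic dose-toxicity model with target 0.25
- DLT probability at 27.5 Gy uniform on (0, 0.25)
- MTD uniform on (27.5, U), with U from 40 to 50 Gy
- one cohort of three treated, no earlier data

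The EWOC dose is the alpha-quantile of the posterior for the MTD. Ranges are over U.

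| Data | EWOC dose, alpha 0.25 | EWOC dose, alpha 0.50 | P(dose given exceeds MTD) |
|---|---|---|---|
| 3/3 at 30 Gy | 27.7 Gy | 28.0 Gy | 0.88–0.93 |
| 3/3 at 32.5 Gy | 27.9 Gy | 28.5 Gy | 0.93–0.96 |
| 2/3 at 30 Gy | 29.0–29.6 Gy | 30.9–34.5 Gy | 0.29–0.42 |
| 2/3 at 32.5 Gy | 29.8–30.3 Gy | 31.4–33.5 Gy | 0.45–0.61 |

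The midpoint between levels -1 and 0 is (27.5 + 30)/2 = 28.75 Gy. Every 3/3 result lies below it, so EWOC assigns level -1 whether one rounds down or to the nearest level. The example would repeat 30 or 32.5 Gy.

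The 2/3 rows give no stable answer. At 30 Gy and alpha 0.25 the dose is nearest to 30 Gy, which is what the example does, but rounding down gives 27.5 Gy. At 32.5 Gy the nearest level is 30 Gy at alpha 0.25 and 32.5 Gy at alpha 0.50.

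**6. How often 3/3 occurs.** At a true DLT rate of 25%, 0.25³ = 1.6% of cohorts. At 40%, 0.40³ = 6.4%.

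**The case against.** The strongest reply is that the intended rule is not in doubt. The Precis, 3.1, 3.2 and 5.2 all name EWOC, 3.1 assigns dose groups by that design, and the conflicting text is labelled an example. An illustration with two branches does not forbid a third, and the paragraph just before it allows de-escalation. Safeguards also remain: investigator review before each dose decision, the grade 5 halt, the PI's power to halt (6.6), and DSMC toxicity summaries (7.2.4). Most of this stands and lowers the severity. It does not remove the defect. The example names the wrong dose for the first patients, and toxicity review comes only after they have been treated.

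Two stronger readings are tempting and are not supported.

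- **That the example also contradicts EWOC after 2/3 DLTs.** The answer depends on the dose, earlier cohorts, alpha, the priors and the rounding convention, and the protocol states no rounding rule. With 0/3 at 30 Gy and then 2/3 at 32.5 Gy, the same model gives 30.4–31.1 Gy at alpha 0.25 (nearest level 30 Gy), but the nearest level is 32.5 Gy under all three values of U (40, 45 and 50 Gy) at alpha 0.40.
- **That 32.5 Gy lies outside the supporting experience.** Section 1.0 reports "HR delivered to a dose of 30 Gy in 5 fractions to be effective and tolerable in a series of 34 patients". The other multi-fraction regimens with a stated dose have BED3 of 24 × (1 + 8/3) = 88 (three fractions) and 24 × (1 + 6/3) = 72 (four fractions). But the institution's own 47-patient series, cited in 3.4.3 as a basis for the starting dose, is described without its doses. Whether it included 32.5 Gy cannot be told.

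**Conclusion.** The point holds on the text alone. The example starts cohort 1 at 32.5 Gy where the design says 30 Gy, and it replaces EWOC with an escalate-or-repeat rule that cannot go down. The firm consequence for later doses is confined to 3/3 DLTs. That case follows from reading the example literally, since it states no count. There the exact lower limit of 29.2% exceeds the 25% target without any prior. The EWOC figures agree but rest on the assumed model and on data from a single cohort. The event is uncommon: 1.6% of cohorts at a 25% DLT rate and 6.4% at 40%.

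A reader might infer that the protocol leaves the dosing rule undecided. It does not, because EWOC is named throughout as the design. This is a drafting error that should be fixed, not a flaw in the design itself.

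**What to change.** In the Example of sequential enrollment, change dose level 1 to dose level 0 (30 Gy). Replace the two escalate-or-repeat sentences with: *The next cohort's level is the one assigned by EWOC from all DLT data (2.1.2), which may be higher, the same or lower, including level -1.*

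This is a wording amendment to one paragraph, with no added patients, time or analysis. It does not touch the MTD definition in 3.8.1 item 8 (at most 2 of 6 patients in a dose group). That definition fits the example's expansion to six, and should be read against EWOC when the amendment is drafted.

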3.3 Therapeutic and Diagnostic Procedures

All simulation and treatment procedures represent current institutional practice and will be the same for all study participants in each dose level

- 3.3.1** Radiation Therapy will consist of partial brain irradiation delivered to the metastatic brain tumor or resection cavity, delivered in 5 treatments with 2-3 treatments delivered per week.
- 3.3.2** CT Simulation will be performed for radiation therapy treatment planning purposes several days prior to the initiation of radiation therapy. This procedure consists of a CT scan performed in the treatment position. It is not for diagnostic purposes and is not itself therapeutic, but the CT image is required for radiation planning and delivery. This procedure is standard of care prior to therapeutic radiation.
- 3.3.3** Pre-treatment and post-treatment MRI of the brain. The patient will be required to undergo diagnostic MRI before and after radiation treatment as well as a treatment planning MRI. MRI will be ordered with and without gadolinium. This diagnostic procedure is standard of care for follow-up of intracranial metastases.

3.4 Radiation Therapy

3.4.1 Required Criteria

1. A high resolution MRI for treatment planning is recommended within 2 weeks of treatment delivery. If using a planning scan, methods for automatically registering the planning scan to the Simulation CT scan must be in place.
2. Utilize frameless stereotactic head immobilization with 6 degrees of freedom (DOF)²⁰ for simulation and treatment delivery.
3. Perform target localization utilizing stereotactic CT scan or MRI
4. Use treatment planning system capable of generating isodose distributions for a given treatment in 3 dimensions
5. Treatment shall be delivered with megavoltage machines of a minimum energy of 6 MV photons. Selection of the appropriate photon energy (ies) should be based on optimizing the radiation dose distribution within the target volume and minimizing dose to non-target normal tissue.
6. Treatment may be delivered with intensity modulated radiation therapy (IMRT) or dynamic conformal arcs (DCA), or via Gamma Knife.
7. Patients must be positioned for each treatment using 3 dimensional imaging ie Cone Beam CT, or comparable patient positioning verification system.

7. Treatment should be initiated within 6 weeks of surgical resection if applicable. It is anticipated that most patients will start within 3 to 4 weeks of surgery
8. Quality analysis of the treatment criteria described in this section (3.4) will be performed by study investigators prior to the patient completing the study treatment.

3.4.2 Target Volume Determination

1. Target volume and isocenter determination will be based on a simulation CT and/or treatment planning MRI (with and without contrast)
2. Stereotactic CT scan slice thickness may not exceed 1 mm
3. Treatment planning MRI slice thickness may not exceed 2 mm
4. The gross target volume (GTV) will include the entirety of the MRI defined T1 post contrast enhancing brain metastasis or the resection cavity including any residual enhancing disease. Surrounding areas of edema will not be considered part of the target volume.
5. A margin of 0.5 mm in all directions will be applied to the GTV to create the clinical target volume (CTV)
6. An additional margin of 1 mm will be added to the CTV to create the PTV.
7. Target volumes (in cc) will be determined for the GTV, CTV and PTV using the treatment planning software

3.4.3 Total dose determination

1. Total dose determination will depend on the currently accruing dose level
2. Starting dose level is based on current institution standards and retrospective reports from other institutions^{15,19}.

Table 1. Summary of dose levels to be tested.

Dose level	Total Dose (Gy)	Dose per Fraction (Gy)	Fraction Number	BED ₁₀ (Early Effects)	BED ₃ (Late Effects)
-1	27.5	5.5	5	44	78
0	30	6	5	49	90
1	32.5	6.5	5	55	103
2	35	7	5	60	117
3	37.5	7.5	5	66	131
4	40	8	5	69	147
SRS*	18-21 Gy	18-21 Gy	1	53-68	126-168

*for comparison only, single fraction SRS will not be used in this protocol

3.4.4 Dose prescription and dosimetry requirements

1. Dose will be prescribed to the isodose line that encompasses the entirety of the PTV.
 1. If intensity modulated radiosurgery (IMRS) is utilized, standard prescription isodose is to 98% (range 95-100%)
 2. If dynamic conformal arcs (DCA) are utilized, standard prescription isodose is to 80% (range 70-90%).
 3. If gamma knife is utilized, standard prescription isodose is to 50%

2. Doses are specified such that at least 95% of the PTV shall receive 100% of the prescribed dose.
 3. Inhomogeneity within the PTV should be kept within $\pm 10\%$ of the prescribed dose, and the minimum dose PTV should be kept within 10% of the dose at the isocenter.
 4. The marginal dose and the 100% dose (isocenter dose) will be recorded for each patient.
 5. For quality control, representative isodose lines (eg. 20%, 40%, 60%, 80%, 90%) must be generated for each patient.
- Quality of PTV coverage will be categorized according to selected isodose line:
1. Total – selected isodose line completely encompasses the PTV
 2. Marginal – selected isodose line incompletely encompasses the PTV, but not by more than 10% of the PTV volume.
 3. Subtotal - selected isodose line incompletely encompasses the PTV, but by more than 10% of the PTV volume. This will not be accepted.
6. Conformality index requirements (ratio of prescription isodose volume to the target volume (PI/TV))
 1. Per protocol if between 1.0 and 2.0
 2. Acceptable variation if ≥ 0.9 but < 1.0 or > 2.0 but ≤ 3.5 .
 3. Unacceptable deviation if > 3.5 .

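### Section 3.4.4 sets PTV homogeneity limits that its own prescription isodoses for dynamic conformal arcs and Gamma Knife cannot meet, so one dose level can carry different doses inside the target

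*Combined protocol and SAP*

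**What the plan says.** Section 3.4.4 fixes the prescription point in item 1: "Dose will be prescribed to the isodose line that encompasses the entirety of the PTV". It then gives a standard line for each technique:

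- IMRS: "standard prescription isodose is to 98% (range 95-100"%).
- DCA: "If dynamic conformal arcs (DCA) are utilized, standard prescription isodose is to 80% (range 70-90"%).
- Gamma Knife: "If gamma knife is utilized, standard prescription isodose is to 50"%, with no range.

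Item 3 has two limits. Inhomogeneity in the PTV should stay within 10% of the prescription in either direction, and "the minimum dose PTV should be kept within 10% of the dose at the isocenter". Neither limit is restricted to a technique. Item 4 identifies the reference for the percentages: "The marginal dose and the 100% dose (isocenter dose) will be recorded for each patient".

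Section 3.4.1 allows intensity modulated treatment, DCA or Gamma Knife. Section 3.3 says that simulation and treatment procedures "will be the same for all study participants in each dose level". Section 3.2 escalates over, and picks the MTD from, the six nominal levels in Table 1 (27.5 to 40 Gy) and does not mention technique. Section 5.3.3 names two strata, intact lesion versus cavity and prior cranial irradiation or none. Technique is not one of them.

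**The concern.** A prescription isodose well below 100% means, by construction, that the isocenter receives well above the prescribed dose. Item 1 builds in such a gradient for DCA and Gamma Knife, while item 3 limits it to 10% for everyone. A plan reviewer applying section 3.4.4 to a standard DCA or Gamma Knife plan cannot satisfy both items.

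The statistical interest is that dose is the experimental variable. Escalation with overdose control (EWOC) treats patients at one level as having had the same dose. If techniques are mixed, they share the dose at the target margin but not the dose inside the target, and nothing in the analysis plan would show this.

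**Working it through.** **Inputs.** Prescription isodoses: item 1 of 3.4.4. Reference (100% = isocenter dose): item 4. Limits: item 3. Dose levels: Table 1 in 3.4.3.

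**Formulas.** Let *i* be the prescription isodose as a fraction of the isocenter dose, with the prescription line just enclosing the PTV.

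- Isocenter dose ÷ prescribed dose = 1/*i*. Item 3 needs 1/*i* ≤ 1.10, so *i* ≥ 1/1.10 = 90.9%.
- Shortfall of the PTV margin below the isocenter = 1 − *i*. Item 3 needs 1 − *i* ≤ 0.10, so *i* ≥ 90%.

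**Each technique against the limits.**

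| Technique and isodose | Isocenter vs prescribed | Margin below isocenter | Limit vs prescription | Limit vs isocenter |
|---|---|---|---|---|
| IMRS 100% | 1/1.00 = 100% | 0% | met | met |
| IMRS 98% (standard) | 1/0.98 = 102.0% | 2% | met | met |
| IMRS 95% | 1/0.95 = 105.3% | 5% | met | met |
| DCA 90% | 1/0.90 = 111.1% | 10% | missed | just met |
| DCA 80% (standard) | 1/0.80 = 125% | 20% | missed | missed |
| DCA 70% | 1/0.70 = 142.9% | 30% | missed | missed |
| Gamma Knife 50% (standard) | 1/0.50 = 200% | 50% | missed | missed |

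The whole IMRS range can meet both limits. The DCA range stops at 90%, below the 90.9% needed, so no line in it meets both. The Gamma Knife standard meets neither.

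These are best-case figures for the margin. Item 2 lets up to 5% of the PTV fall below the prescribed dose, which can only lower the PTV minimum.

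**What this means in Gy at the isocenter (prescribed dose ÷ *i*).**

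| Level | IMRS 98% | DCA 80% | Gamma Knife 50% |
|---|---|---|---|
| 0 (30 Gy) | 30/0.98 = 30.6 | 30/0.80 = 37.5 | 30/0.50 = 60 |
| 4 (40 Gy) | 40/0.98 = 40.8 | 40/0.80 = 50 | 40/0.50 = 80 |

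The prescribed marginal dose in each row is the same for all three techniques.

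**The case against.** The conflict between items 1 and 3 is hard to dispute, but several stronger conclusions that a reader might draw from it do not stand.

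- *Every DCA or Gamma Knife plan is a protocol violation.* Item 3 is worded as a recommendation and has no deviation class, unlike the coverage categories in item 5 and the conformality index in item 6. The text does not say how a departure from item 3 is to be classified.
- *The order of the dose levels is lost.* This is true only of isocenter dose. A level is defined by the dose at the line enclosing the PTV, which is common to all techniques and rises at every step of Table 1.
- *The technique gap exceeds the whole escalation.* Setting the gap between Gamma Knife and IMRS at level 0 (60 − 30.6 = 29.4 Gy) against the 10 Gy rise in prescribed dose from level 0 to level 4 mixes two quantities. At the isocenter that rise is 10.2 Gy for IMRS (40.8 − 30.6), 12.5 Gy for DCA (50 − 37.5) and 20 Gy for Gamma Knife (80 − 60). The gap between DCA and IMRS at level 0 is 6.9 Gy (37.5 − 30.6), smaller than any of these. The extreme figures come from Gamma Knife alone.
- *DLTs are confounded with technique.* That would need technique to vary with dose level, and the documents give no technique mix. Nor do they link isocenter dose to CNS toxicity. The PTV adds only 0.5 mm plus 1 mm to the GTV (3.4.2), and the normal-tissue limits in Table 2 apply whatever the technique.
- *Section 3.3 forbids mixing techniques.* Its sentence introduces a list of radiation in five treatments, CT simulation and MRI, and does not name delivery technique. It is ambiguous, not a clear contradiction.

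There are also partial safeguards: treatment parameters are collected (3.8.4), investigators check the section 3.4 criteria before treatment is completed (3.4.1), and radiation oncologists outside the study team review plans (7.2.3). What remains is that these checks would apply a section whose items disagree, and that no planned analysis uses the recorded isocenter dose.

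**Conclusion.** Section 3.4.4 cannot be followed as written for two of the three permitted techniques at their standard isodoses. At the isocenter, DCA at 80% is 25% and Gamma Knife at 50% is 100% above the prescription, against a stated 10%; DCA at the 90% end of its range narrowly misses, at 11.1%. This rests on the protocol's own figures, on item 4's equation of 100% with the isocenter dose, and on the isocenter lying within the PTV.

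The statistical consequence is conditional. If more than one technique is used, EWOC and the MTD pool plans with the same marginal dose but different interior doses, with no analysis by technique. The technique mix and the effect on DLT risk cannot be derived from the documents, so this is a risk of heterogeneity within a level and not a demonstrated bias in the MTD. If only IMRS is used, the pooling issue falls away, but nothing in the protocol ensures that.

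**What to change.** The clinical team should reconcile items 1 and 3 of 3.4.4 with the techniques permitted in 3.4.1, and state whether the sentence in 3.3 on identical procedures within a dose level covers delivery technique. I take no view on which requirement should stand.

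If more than one technique remains:

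- report the MTD as a prescribed marginal dose together with the prescription isodose and technique used;
- add to 5.3 a descriptive table of DLTs by dose level and technique, showing the isocenter dose already recorded under item 4.

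The cost is protocol wording and one table, with no new data collection and no change to the EWOC design. The downside is small cells: 24 patients spread over up to six levels and three techniques can describe heterogeneity but not test for it.
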